 - a. HA group will receive one 6 mL injection of low molecular weight (average 500,000-730,000 dalton) HA preparation, Hyalgan (Fidia Farmaceutici S.p.A., Abano Terme, Italy). Needle guidance and injection will be performed under ultrasound to the affected glenohumeral joint, posterior approach, by a fellowship-trained physician. The syringe will be covered with an opaque shield to blind both the patient and treating physician.
 - b. PRP group will undergo the same above procedure as the HA group in respect to ultrasound guidance, anatomic approach, and double blinding. The Harvest Technologies Corporation (Plymouth, MA) SmartPReP Clear PRP preparation kit and machine will be used to prepare the samples in accordance with manufacturer

instructions. Venipuncture and blood collection, PRP centrifuge, final PRP preparation, and covering of the syringe with an opaque shield will be performed in a sterile manner by a trained study team member not involved in the direct care and management of the study subjects. Final PRP samples will aim to be leukocyte reduced. Prior to injection, each sample in the PRP group will be sent to the laboratory for hemoglobin / hematocrit, WBC, and platelet counts. 6 mL PRP will be injected.

2. In order to ensure that the treating physician is blinded to the treatment study subjects receive, the treating physician will perform ultrasound guidance and needle placement, but an Interventional Spine and Sports Medicine fellow or a Physiatry attending not involved in the study will prepare and perform the actual injection.
3. Post procedure:
 - a. Patients will be instructed to take acetaminophen 500 mg every 6 hours (maximum of 3 gms) for pain relief as needed.
 - b. Ice applied over the affected joint will not be allowed for 3 days and NSAIDs are to be avoided for at least 6 weeks after the intervention is performed due to their anti-inflammatory properties.
 - c. Patients will be instructed to avoid taking baths and swimming in order to minimize risk of infection. Showers are allowed. Patients can continue their usual activities of daily living, as tolerated.
 - d. Follow-up questionnaires will be administered at 1, 2, 3, 6, and 12 months post-injection.

Sample size analysis and statistical analysis plan:

Proposed analysis: Two-way repeated measures ANOVA

Alpha level: 0.05

Beta or power level: 0.861

Primary outcome variable estimate: SPADI

Number of groups being compared: 2

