Effect size or change expected between groups: 10-point change (± 15)

Resulting number per group: 30

Total sample size required: 70

Descriptive analyses of the patient population will include reporting means (with standard deviations) for continuous variables and frequencies (with percentages) for discrete variables. Prior to initiation of inferential analyses, data will be evaluated for completeness and, for continuous measures, normality. Comparative differences between the study groups will be evaluated using independent samples t-test for continuous variables and chi-square/Fisher's exact test for categorical variables. This will include comparisons of patient characteristics as well as baseline patient reported outcomes and all range of motion measures. Factors that do not meet the assumption of normality will be analyzed using the non-parametric equivalents.

The primary outcome in this study is the total SPADI score and the longitudinal assessment of that score over four follow-up time points after baseline. A systematic review by Roy et al

(Arthritis Rheum, 2009) found that the minimal clinical important difference (MCID) for patients with general shoulder pain ranged between 8 and 13 points. Williams et al. (J Rheumatol, 1995) found that changes in the SPADI score between +10 and -10 points were not able to distinguish between shoulder patients whose condition improved, remained the same, or worsened. In a similarly designed study looking at the effect of intra-articular corticosteroids and supervised physiotherapy, Carette et al. (Arthritis & Rheumatism, 2003) used a 10-point change as their MCID. Given those estimates, we calculated our sample size based on the ability to detect a similar 10-point change between treatment groups in the total SPADI scores.

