Group sample sizes of 25 patients in each treatment group of the study will achieve 86% power to detect an MCID of 10 points in the total SPADI score between groups with an estimated standard deviation of ± 15 points in a two-way repeated measures ANOVA design with statistical significance set to alpha equal to 0.05. To adjust for any loss of patients due to early withdrawal, we will increase our sample size by 20% for group sample sizes of 30 and a total sample size of 70 patients. All analyses will be based on an intent-to-treat model, and any missing data will be imputed using a last observation carried forward methodology. Mixed models will also be generated to adjust for any effects of potential confounding from age, sex, and other factors. Longitudinal assessment of the other patient reported outcomes will also be evaluated using similar statistical models.

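### Last observation carried forward is the only missing-data method and no sensitivity analysis is planned, so the PRP-HA comparison can be biased if dropout, or change after dropout, differs between arms

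*Combined protocol and SAP*

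**What the plan says.** All of this is in the section on sample size and statistical analysis unless stated otherwise.

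- Missing data: "All analyses will be based on an intent-to-treat model, and any missing data will be imputed using a last observation carried forward methodology". No other missing-data method and no sensitivity analysis appears anywhere in the document.
- Withdrawal is expected: "To adjust for any loss of patients due to early withdrawal", the plan says, "we will increase our sample size by 20% for group sample sizes of 30 and a total sample size of 70 patients".
- Before analysis, "data will be evaluated for completeness and, for continuous measures, normality". Nothing follows from the result of the completeness check.
- A second model is planned: "Mixed models will also be generated to adjust for any effects of potential confounding from age, sex, and other factors". Its stated purpose is covariate adjustment. Nothing says that it uses unimputed scores.
- The primary outcome is total SPADI and the "longitudinal assessment of that score over four follow-up time points after baseline", analysed by two-way repeated measures ANOVA. Study procedures, item 3d, lists five visits: "Follow-up questionnaires will be administered at 1, 2, 3, 6, and 12 months post-injection".
- The secondary outcome list gives a baseline assessment for ASES and the two pain scores, but not for patient satisfaction or side effects.

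**The concern.** Last observation carried forward (LOCF) assumes that a patient who leaves would have kept the last recorded score to month 12. The last two visits are six months apart. A month-1 score could stand in for eleven months, and a patient lost before month 1 has the baseline score entered at every visit. These flat stretches go straight into the longitudinal primary test.

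Depending on when and from which arm patients leave, and on how scores move afterwards, LOCF can be harmless, can shrink or enlarge a real PRP-HA difference, or can create a group-by-time effect that does not exist. With no second missing-data analysis, a reader of the results could not tell which of these applies.

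**Working it through.** **Inputs from the plan.** Difference 10 points, SD 15, alpha 0.05, 25 evaluable per group, stated power 0.861; 30 per group but 70 in total; 1:1 allocation; visits at months 1, 2, 3, 6 and 12.

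**Assumed, because the documents are silent.** Dropout by arm and its timing, score trajectories, and within-patient correlation (0.4 to 0.8).

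**1. The plan's own power figure.** At a single time point, 10 / (15 × √(2/25)) = 2.357, and 2.357 − 1.960 = 0.397, which gives 65.4% two-sided. For a group test on the average of T scores the SD becomes 15 × √((1 + (T − 1)ρ)/T). That reaches 86.1% at ρ of about 0.43 (T = 4), 0.47 (T = 5) or 0.49 (T = 6). The plan states no correlation, so 86% is plausible but cannot be confirmed. The LOCF point does not depend on it.

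**2. Loss covered by the allowance.** 1 − 25/30 = 16.7%. If the total of 70 means 35 per group, 1 − 25/35 = 28.6%.

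**3. Bias formula.** With dropout random within arm, the LOCF bias in the month-12 PRP-HA difference is

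d_P(L_P − F_P) − d_H(L_H − F_H),

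where d is the share lost, L the mean at the last observation and F the mean at month 12 had the patients stayed. It is zero if L = F in both arms (flat scores), or if d and L − F are the same in both arms.

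**4. Dilution with equal dropout.** The estimate is 10 × (1 − d) if all loss precedes month 1 and the difference is constant from month 1, or if the difference is 0 at month 3, reaches 10 at month 12, and all dropout follows month 3.

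| Setting | 16.7% loss | 28.6% loss |
|---|---|---|
| All loss before month 1, or late divergence | 10 × (1 − 1/6) = 8.3 | 10 × (1 − 2/7) = 7.1 |
| One fifth of loss before month 1, difference constant from then | 10 × (1 − 0.167/5) = 9.7 | 10 × (1 − 0.286/5) = 9.4 |
| Constant difference, flat scores, dropout after month 3 | 10.0 | 10.0 |

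**5. False signal with unequal dropout.** Take no true effect, 10% against 30% dropout after month 3, and a shared rebound of 5, 10 or 15 points, half of it reached by month 6. The month-12 bias is (0.30 − 0.10) × rebound = 1, 2 or 3. The five-visit average is biased by 1.5 × (1, 2, 3) / 5 = 0.3, 0.6 or 0.9.

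**6. A constant difference is not enough.** Add a constant 10-point PRP advantage to step 5 with the 15-point rebound. If HA loses 30% and PRP 10%, the month-12 estimate is 10 − 3 = 7.0. With the rates swapped it is 10 + 3 = 13.0.

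**7. Effect on the planned ANOVA.** Simulation: 8,000 runs per setting, 30 or 35 per arm, SD 15, compound symmetry, correlation 0.4 to 0.8, Greenhouse-Geisser correction. Under step 5 the group-by-time type I error was about 5-6%, 6-11% and 8-20% for rebounds of 5, 10 and 15 points. With equal 20% dropout and a shared 15-point rebound it was 4.1-5.0%.

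**8. Month-12 power, illustrative only.** The plan names no month-12 contrast. At correlation 0.6 (30 / 35 per arm), with a constant difference, flat scores and equal dropout after month 3, LOCF had 88% / 93% against 81% / 83% for a likelihood model on observed scores. With late divergence the order reversed: 72.5% / 66.3% against 80.8% / 82.2%.

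**9. Dropout that depends on the score.** With a constant 10-point difference and dropout driven by the month-3 score, LOCF gave 10.1-10.4 and the observed-data model 10.0-10.1. When the unseen month-12 score drove dropout, LOCF gave 9.6-9.9 and the observed-data model 9.1-9.7.

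**10. Outcomes without a baseline.** A patient with no follow-up has no satisfaction or side-effect value to carry forward, so the rule is undefined there.

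**The case against.** The strongest defence is that LOCF need not do harm. With equal dropout and flat scores it is unbiased and can be the more powerful choice (steps 4 and 8). A likelihood analysis rests on missing at random and does no better when dropout depends on unseen scores (step 9). The larger illustrations need strong inputs: the 20% type I error takes a threefold dropout imbalance, a rebound of one SD and correlation 0.8, none of which the documents suggest. The mixed models might also have been meant for observed data. All of this stands, but none of it gives the reader a way to find out which situation the trial is in.

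Four readings go too far:

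- *That a real effect will fall below the minimal important difference.* The cited range "ranged between 8 and 13 points" is used to choose the sample size; the plan does not compare estimates with it. The value of 7.1 needs 28.6% loss, all of it before month 1 or before any difference appears. The 25-to-30 allowance gives 8.3 even then.
- *That LOCF is safe once the between-group difference is constant.* Step 6 shows otherwise; equal dropout or flat scores are needed too.
- *That the month-12 power figures describe the primary test.* They do not.
- *That the mixed models are certain to use imputed data.* A literal reading of the LOCF sentence covers them, but the text does not settle it.

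**Conclusion.** The concern holds in conditional form and should be fixed. LOCF is the only missing-data method stated, it applies to every analysis, withdrawals are expected, and nothing planned would reveal its effect. Under random dropout it biases the comparison when mean scores change differently in the two arms after dropout, or when dropout differs between arms while scores are changing. It does not when dropout rate, timing and later change are shared, or when scores are flat after dropout.

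Under the assumed inputs the month-12 effect runs from none to a loss of 2.9 points out of 10 with equal dropout, and to 3 points in either direction with 10% against 30% dropout and a 15-point rebound. The bias in the five-visit average is smaller, 0.9 points in that last setting. These figures show what LOCF can do. The direction and size in this trial cannot be known from the documents.

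**What to change.** - Drop LOCF as the primary method. Fit the mixed model already planned (group, visit, group-by-visit, baseline SPADI) by likelihood to all observed follow-up scores of randomised patients, as randomised, without imputation. First reconcile the four follow-up points with the five visits.
- Amend the proposed-analysis line and the ANOVA power sentence to match, so that there are not two primary analyses. Before unblinding, name the contrast that tests the hypothesis and restate power for it.
- Report missing data by arm and visit, including patients with no follow-up score.
- Add at least one sensitivity analysis that includes those patients and departs from missing at random, for example multiple imputation with imputed scores made worse in one arm at a time. LOCF may stay as a further sensitivity analysis.
- Treat ASES and the pain scores in the same way. For satisfaction and side effects, report numbers observed and missing by arm.

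**Cost.** Text and analysis code only; no new data or patients. The primary analysis then relies on missing at random, intervals may be somewhat wider (in the constant-difference and late-divergence settings of step 8 the LOCF month-12 estimate had a 7-15% smaller standard deviation), month-12 power is lower where the difference was already constant and dropout equal, and there is no advantage when dropout depends on unseen scores. If the data are already unblinded, which the documents do not say, the same analyses can be reported and labelled as post hoc.
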